Protocol:**Study Title:**

The effect of perineal wound infection on the anal sphincter

A prospective observational study evaluating the sonographic appearance of the anal sphincter in postpartum women with perineal wound infection.

Chief Investigator:

[name] [name], MD FRCOG
Consultant Obstetrician & Gynaecologist
Croydon Health Services
[name]
Croydon, United Kingdom
[contact]

Clinical Investigation Plan Synopsis

Study Title	A prospective observational study evaluating the sonographic appearance of the anal sphincter in postpartum women with perineal wound infection.
IRAS Number	278466
Study Design	Prospective observational study
Study Participants	Women referred to the Croydon University Hospital perineal clinic with perineal wound infection following vaginal delivery
Planned Sample Size	80 (seen in year and patients agreeing to participate and exclusion criteria)
Planned Study Period	Until wound healed
	Objectives
Primary	To investigate the clinical progression of perineal wound infection
Secondary	
 1. To investigate whether perineal wound infection can extend to involve an intact anal sphincter 2. To investigate the integrity of the anal sphincter in women with a repaired obstetric anal sphincter injury and perineal wound infection.
Inclusion Criteria	
 - Women with childbirth related perineal injury/episiotomy and wound infection - Women over 18 years of age - Ability to understand and read the patient information sheet (in English) - Ability to give informed consent
Exclusion Criteria	
 - Vulnerable Adult - Fetal or neonatal death or poor neonatal outcome - Women who are in an immunosuppressive state (e.g human immunodeficiency virus or pharmacologically induced immunodeficiencies by chemotherapy or steroids) - Inability to give consent

TABLE OF CONTENTS

5.2.2 Subject Data Protection
6. INVESTIGATION TIMETABLE AND TERMINATION
7. LITERATURE REVIEW AND REFERENCES

1. INTRODUCTION

In the United Kingdom (UK), 85% of women sustain perineal injury following a vaginal delivery, which accounts for over 350,000 women annually. Injury is either spontaneous, iatrogenic following episiotomy or a combination of the two, with 69% of these wounds subsequently requiring surgical repair (suturing)(1,2).

The perineum can be divided into two parts; the urogenital triangle which contains the external genital organs and the anal triangle containing the anal sphincter and canal(3). Spontaneous perineal injury can therefore be classified as shown below in Table 1. This differentiation to be made between injuries which involve external anal sphincter (EAS), internal anal sphincter (IAS) and anal mucosa(4).

Degree	Injury
First	Skin only
Second	Perineal muscles but not involving the anal sphincter
Third	Anal sphincter complex 3a- less than 50% of the external anal sphincter 3b- more than 50% of the external anal sphincter 3c- internal anal sphincter torn
Fourth	Anal sphincter complex and anal mucosa

Perineal injury following childbirth can however result in complications such as wound infection. Signs and symptoms associated with perineal wound infection including, increasing pain, swelling, erythema, excessive or offensive discharge, fever and wound dehiscence(5). Croydon Health Services has its own dedicated perineal clinic to manage women with perineal wound complications following childbirth. The incidence of perineal wound infection between January 2016 to September 2017 was 22.6%(6). In addition, in 2019, 120 women attended perineal clinic for review and management of symptoms suggesting perineal wound infection.

Endoanal ultrasound has been shown to be useful in the assessment of obstetric anal sphincter injury (OASI)(7). The anal sphincter can also be visualised using multiplanar transperineal ultrasound(three/four-dimensional)(8). However, the natural history and integrity of the anal sphincter in women with OASI and wound infection has never been evaluated.

In addition, wound infection can extend to affect deeper tissues (9). It is not known whether this infection can infiltrate an intact anal sphincter.

Understanding the natural history of perineal wound infections would enable appropriate interventions prior to the development of complications such as anal incontinence.

2. STUDY HYPOTHESIS, AIMS AND OBJECTIVES

Aim

To evaluate the sonographic appearance of the anal sphincter complex in women with perineal wound infections using three-dimensional (3D) endoanal ultrasound.

Objectives

Primary:

To investigate the clinical progression of perineal wound infection

Secondary:

3. To investigate whether perineal wound infection can extend to involve an intact anal sphincter
4. To investigate the integrity of the anal sphincter in women with repaired obstetric anal sphincter injury who sustain perineal wound infection.

4. METHODOLOGY

4.1 Overall Design

This is a single prospective observational study to assess the appearance of the anal sphincter complex in women with wound infection following childbirth related perineal injury using (3D) endoanal ultrasound or multi-planar transperineal ultrasound(3D/4D).

All patients who have been referred to the Croydon University Hospital dedicated perineal clinic with perineal wound infection will be invited to participate. All patients will be given a patient information sheet describing the study prior to consent. Patients will be given time to read the information included and time to discuss with relatives, colleagues and carers. In addition, time to ask the recruiter any questions that have arisen after reading the consent form. Informed consent will be obtained. Patients will be assessed at weekly intervals until the wound infection has resolved and the wound has clinically healed. At follow-up all patients will complete a case report form, have a vaginal, perineal and rectal examination. Following this, the wound will be photographed with the MolecuLight i:X Imaging Device: a portable, non-invasive, real-time camera used to depict the bacterial load of a wound. In addition, in perineal wounds that have superficially dehisced, wound healing progression will be mapped using the Silhouette® 3D camera: an imaging device that precisely and consistently measures the area, depth, volume of wounds and their healing progress. Finally, an endoanal ultrasound scan and/or transperineal ultrasound will be performed.

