4.2 Procedures and Assessment

Patient data, history and physical examination:

As per standard procedure for the Croydon Health Services Perineal Clinic. Demographic and obstetric data will be collected prospectively from the maternity notes, including: maternal age, gestational age at delivery, parity, body mass index, duration of first and second stage of labour, indication for operative vaginal delivery, mode of delivery, mediolateral episiotomy, and neonatal weight. In addition, information in regards to the repair of the perineal injury including suture type, place of repair and grade of repairer. Presenting symptoms review, medical history, use of medications including antibiotics for wound infection will be obtained at baseline. Women will have a vaginal, perineal and rectal examination prior to ultrasound scan. This be recorded on the case report form.

All datasets will be coded and anonymised. The data will be stored in a secure room within the Trust. All electronic data will be stored within password protected IT system within the Trust, which is only accessible by the clinical and research team.

Endoanal Ultrasound

Endoanal ultrasound will be performed with the BK Flexfocus 400 (Gentofte, Denmark) fitted with a 12 - 16 MHz anorectal transducer (type 2050; focal point up to 20 mm and focal range 5 - 45 mm). Patients will be scanned in the left lateral position, with the endoanal probe along the axis of the anal canal.

Anal sphincter defects will be scored using a validated Starck score which accounts for depth, length and size of the defect for both internal and external anal sphincter, with a range from 0 being no defect to 16 being maximal defect.

Transperineal Ultrasound

If endoanal ultrasound is declined or not tolerated, the anal sphincter will also be assessed using three-/four-dimensional (3D/4D) transperineal ultrasound using a Voluson 730 Expert or Voluson S6 systems with a RAB 8–4-MHz transducer (GE Medical Systems, Zipf, Austria) with the probe placed externally on the area of the fourchette. Patients will be scanned in a dorsal lithotomy position with hips in a flexed and slightly abducted position. Advantages of this form of ultrasound include acceptability by patients as it is painless and non-intrusive(7,8).

Microbiological assessment:

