If a wound swab has not been taken prior to referral or wound swab results are not available, one will be taken to detect the causative organisms. Appropriate antibiotics will then be given to cover the detected organism.

The Silhouette® 3D camera:

For wound that have superficially dehisced, the wound surface area, depth, volume and healing progress will be precisely measured using the Silhouette® 3D camera. This is a system that uses 3D laser technology to track wound healing progression.

The MolecuLight i:X:

The bacterial load of the perineal wound will be measured every week using the MolecuLight i:X. This is a system, which uses fluorescent illumination to capture and document the presence of bacteria. The fluorescence images obtained have distinct colours, which are associated with bacteria and other different wound aspects (Table 1). These findings will be supported by microbiological analysis of the wound with swab culture and sensitivity.

Table 1:

Red	Presence of potentially harmful levels of bacteria
Green	Connective tissues in skin
Dark/black areas	Blood, highly vascularized tissues, necrotic tissue, highly pigmented tissue (freckles, moles, etc.) or poorly illuminated areas
White	Materials in the field of view that are white (bed sheet, clothing, paper, wound measuring ruler, etc.) or oversaturation of color signal
Cyan	Presence of Pseudomonas aeruginosa

Statistical analysis

Statistical analysis will be performed using SPSS version 20.0 or higher.

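### Does ending the ultrasound assessments at wound healing leave the question about the intact sphincter without an adequate scan schedule?

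*Combined protocol and SAP*

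**What the plan says.** The synopsis gives the study period as "Until wound healed". Section 4.1 sets the visits: "Patients will be assessed at weekly intervals until the wound infection has resolved and the wound has clinically healed". It then lists what is done at follow-up: case report form, examination, MolecuLight photograph, and Silhouette mapping for superficially dehisced wounds. The list ends: "Finally, an endoanal ultrasound scan and/or transperineal ultrasound will be performed".

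Section 4.2 describes the baseline history and then adds: "Women will have a vaginal, perineal and rectal examination prior to ultrasound scan". It gives no interval for ultrasound, whereas for bacterial imaging it says: "The bacterial load of the perineal wound will be measured every week using the MolecuLight i:X". Transperineal ultrasound is the fallback modality: "If endoanal ultrasound is declined or not tolerated, the anal sphincter will also be assessed using".

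The two secondary objectives in section 2 are "To investigate whether perineal wound infection can extend to involve an intact anal sphincter" and "To investigate the integrity of the anal sphincter in women with repaired obstetric anal sphincter injury who sustain perineal wound infection". The contents list names a section 6 on the timetable. Its text is not in the copy reviewed, so this reading rests on the sections available.

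**The concern.** Two features together look like a gap. First, a weekly frequency is written out for the MolecuLight but not for ultrasound, and no scan is labelled as the baseline or final one. Second, follow-up closes at healing, so a sphincter change that first appears at that visit has no later study scan to support or contradict it.

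The first secondary objective is about whether something can happen, so one or a few positive women might be taken as the answer. If one of those positives is a single misread scan on the last day, the study could report extension of infection that did not occur. A scan not taken before follow-up closes cannot be obtained later, which would be a reason to act before recruitment ends.

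**Working it through.** **Reading the schedule.** In section 4.1 the weekly interval, the list of follow-up procedures and the ultrasound stand in one paragraph, in that order. The natural reading is an ultrasound at every weekly visit up to and including the healing visit. Section 4.2 places a scan after the examination, directly following the baseline history, which implies a scan at entry. No section describes scanning only at entry and at healing. The explicit weekly wording for the MolecuLight does not take ultrasound off the visit list.

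**Inputs.** The plan gives one number that matters here, 80 women (section 4.5). It is a headcount from clinic attendance (80/120 = 67%), so there is no power or precision figure to reproduce. The rest is assumed:
- Healing time T is lognormal with median 4 weeks and log-SD 0.6.
- Follow-up scans number m = T rounded up, with mean 5.3.
- All 80 women are intact at first scan. This is a ceiling, since women with repaired sphincter injury are also enrolled.
- There is no true change. False-positive rate per scan is p = 5% or 2%, with within-woman correlation ρ = 0, 0.2, 0.5 or 0.8 (beta-binomial).

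**Formulas.** With a = p(1/ρ − 1) and b = (1 − p)(1/ρ − 1), the chance that a woman with a negative first scan is first positive at her last scan is q = E[B(a+1, b+m)/B(a, b)]/(1 − p). For ρ = 0 this is E[(1 − p)^(m−1) p]. The chance of at least one such woman is 1 − (1 − q)^80.

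Example with p = 5%, ρ = 0, m = 4: 0.95³ × 0.05 = 0.0429, or 3.4 of 80. Averaged over the healing curve it is 3.25 of 80, so q = 0.0406 and 1 − 0.9594^80 = 96%.

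**False defects first seen at the last visit, weekly scans, p = 5%**

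| ρ | Any false defect, of 80 | First seen at last visit | Share | At least one woman |
|---|---|---|---|---|
| 0 | 18.3 | 3.25 | 18% | 96% |
| 0.2 | 11.0 | 1.69 | 15% | 82% |
| 0.5 | 5.5 | 0.73 | 13% | 52% |
| 0.8 | 1.9 | 0.23 | 12% | 20% |

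At p = 2% the last column is 77%, 51%, 26%, 9%, and the shares run from 12% to 19%. With 40 women intact and p = 5% it is 81%, 57%, 31%, 11%.

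**Does a scan after healing help?** Among women first positive at the last visit, the chance that any is positive again on one repeat is 15%, 20%, 13%, 5% (p = 5%). Set against 96%, 82%, 52%, 20%, that looks like a large gain, but it covers only the last-visit women. The study-wide quantity is the chance that at least one of the 80 has a false defect confirmed, meaning that her first positive scan is followed by a second positive:

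| ρ | p = 5%, no repeat | p = 5%, with repeat | p = 2%, no repeat | p = 2%, with repeat |
|---|---|---|---|---|
| 0 | 53% | 60% | 12% | 15% |
| 0.2 | 78% | 83% | 43% | 48% |
| 0.5 | 72% | 76% | 39% | 43% |
| 0.8 | 44% | 46% | 20% | 22% |

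The repeat raises every figure slightly, because it gives each last-visit false positive a chance to be confirmed that it would not otherwise have. The fall in unrepeated findings comes from the rule that a change seen once is unconfirmed, and that rule needs no new scan.

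**What the repeat would add.** If true change arises at h a week until healing, the expected total is 80 × E[1 − (1 − h)^m], and the number first seen at the last scan is 80 × E[(1 − h)^(m−1) h]. At h = 1% these are 4.1 and 0.8; at h = 2%, 8.0 and 1.5. The other 3.3 (4.1 − 0.8) and 6.5 (8.0 − 1.5) women are first seen earlier and already have a later study scan.

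**The case for a change.** The strongest case for acting is that detection is not confirmation. For a question of whether something can happen, a positive seen once is the weakest evidence, and the missing scan is lost for good once follow-up ends. The remedy would also be small. With weekly scans, false and true last-visit changes together come to about 1 woman (0.2 + 0.8) to 5 women (3.2 + 1.5) of 80.

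If women were in fact scanned only at entry and at healing, every change would be unrepeated. The chance of at least one false change at 5% error would then be 98%, 96%, 87% or 55% across the four correlations.

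Part of this stands. A last-visit change is observed once and cannot be followed, and if the only true extension in the cohort appeared on that day, the study would have to report it as unconfirmed. The ultrasound frequency could also be written more plainly. The rest is weaker. The entry-and-healing schedule has no basis in the text. A last-visit change is still seen and scored, so it is not lost to the objective. The extra scan is an added research procedure whose benefit is confined to about one true late change, and it does nothing to reduce confirmed false ones.

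**Conclusion.** No change to the plan is needed. The plan implies weekly ultrasound up to healing, which is a reasonable window for asking whether an active wound infection reaches the sphincter. The unwritten frequency is a gap that the site and the analyst would fill in the obvious way. New changes can be reported within modality as repeated or seen once, with last-visit changes in the second group; that choice remains open at analysis.

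The true limitation is modest: about 12-19% of false defects, and under one to about one and a half true changes in 80 women, would first appear at the last visit. A post-healing scan would move the chance of at least one confirmed false defect from 78% to 83% (5% error, correlation 0.2), so it offers no protection against a wrong answer to a secondary question.

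The healing curve, error rates, correlations, weekly rate of true change and number intact are all assumed, and the absolute figures vary widely with them. The direction of the repeat-scan result does not: under this confirmation rule, an extra scan can only add confirmed findings, true or false.

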4.2 Procedures and Assessment

Patient data, history and physical examination:

As per standard procedure for the Croydon Health Services Perineal Clinic. Demographic and obstetric data will be collected prospectively from the maternity notes, including: maternal age, gestational age at delivery, parity, body mass index, duration of first and second stage of labour, indication for operative vaginal delivery, mode of delivery, mediolateral episiotomy, and neonatal weight. In addition, information in regards to the repair of the perineal injury including suture type, place of repair and grade of repairer. Presenting symptoms review, medical history, use of medications including antibiotics for wound infection will be obtained at baseline. Women will have a vaginal, perineal and rectal examination prior to ultrasound scan. This be recorded on the case report form.

All datasets will be coded and anonymised. The data will be stored in a secure room within the Trust. All electronic data will be stored within password protected IT system within the Trust, which is only accessible by the clinical and research team.

Endoanal Ultrasound

Endoanal ultrasound will be performed with the BK Flexfocus 400 (Gentofte, Denmark) fitted with a 12 - 16 MHz anorectal transducer (type 2050; focal point up to 20 mm and focal range 5 - 45 mm). Patients will be scanned in the left lateral position, with the endoanal probe along the axis of the anal canal.

Anal sphincter defects will be scored using a validated Starck score which accounts for depth, length and size of the defect for both internal and external anal sphincter, with a range from 0 being no defect to 16 being maximal defect.

Transperineal Ultrasound

If endoanal ultrasound is declined or not tolerated, the anal sphincter will also be assessed using three-/four-dimensional (3D/4D) transperineal ultrasound using a Voluson 730 Expert or Voluson S6 systems with a RAB 8–4-MHz transducer (GE Medical Systems, Zipf, Austria) with the probe placed externally on the area of the fourchette. Patients will be scanned in a dorsal lithotomy position with hips in a flexed and slightly abducted position. Advantages of this form of ultrasound include acceptability by patients as it is painless and non-intrusive(7,8).

Microbiological assessment:

If a wound swab has not been taken prior to referral or wound swab results are not available, one will be taken to detect the causative organisms. Appropriate antibiotics will then be given to cover the detected organism.

The Silhouette® 3D camera:

For wound that have superficially dehisced, the wound surface area, depth, volume and healing progress will be precisely measured using the Silhouette® 3D camera. This is a system that uses 3D laser technology to track wound healing progression.

The MolecuLight i:X:

The bacterial load of the perineal wound will be measured every week using the MolecuLight i:X. This is a system, which uses fluorescent illumination to capture and document the presence of bacteria. The fluorescence images obtained have distinct colours, which are associated with bacteria and other different wound aspects (Table 1). These findings will be supported by microbiological analysis of the wound with swab culture and sensitivity.

Table 1:

Red	Presence of potentially harmful levels of bacteria
Green	Connective tissues in skin
Dark/black areas	Blood, highly vascularized tissues, necrotic tissue, highly pigmented tissue (freckles, moles, etc.) or poorly illuminated areas
White	Materials in the field of view that are white (bed sheet, clothing, paper, wound measuring ruler, etc.) or oversaturation of color signal
Cyan	Presence of Pseudomonas aeruginosa

Statistical analysis

Statistical analysis will be performed using SPSS version 20.0 or higher.

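### Nothing in the plan masks whoever scores the sphincter scans to the examination, the sphincter status at delivery or the visit order, so both sphincter objectives are open to reading bias

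*Combined protocol and SAP*

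**What the plan says.** Section 4.2, in the text on history and examination, states: "Women will have a vaginal, perineal and rectal examination prior to ultrasound scan". Section 4.1 gives the same order at follow-up. The case report form and examination come first, then the fluorescence photograph, then 3D wound mapping where the wound has opened. The scan closes the visit: "Finally, an endoanal ultrasound scan and/or transperineal ultrasound will be performed". On timing: "Patients will be assessed at weekly intervals until the wound infection has resolved and the wound has clinically healed". The number of scans per woman is therefore not fixed.

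The sphincter measure is in section 4.2: "Anal sphincter defects will be scored using a validated Starck score which accounts for depth, length and size of the defect", on a scale from 0 to 16. It appears only under endoanal ultrasound. Transperineal ultrasound, the fallback when endoanal scanning is refused or not tolerated, has no scoring method.

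The two secondary objectives in section 2 are "To investigate whether perineal wound infection can extend to involve an intact anal sphincter" and "To investigate the integrity of the anal sphincter in women with repaired obstetric anal sphincter injury who sustain perineal wound infection". Delivery data include "information in regards to the repair of the perineal injury including suture type, place of repair and grade of repairer". The degree of tear is not itself a listed item. The two objectives nevertheless divide women by sphincter status at delivery, so the team must know it.

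Sections 4.1, 4.2 and 4.4 do not mention who scores, when scoring happens, masking, random-order reading, repeat reading or reader agreement.

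**The concern.** Scoring depth, length and size of a defect on an image takes judgement. A reader who knows that the wound is deep and infected, that the sphincter was repaired at delivery, or what was scored last week has expectations that can colour the reading. The study has one group, so no comparison arm exists in which such an effect would show or cancel.

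The stated aim is sonographic appearance, and both secondary objectives are answered from these readings. The first is especially exposed because it asks whether something can happen at all. A handful of images read as newly abnormal would turn the answer from not seen to seen. A handful of real changes read as normal would do the reverse.

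**Working it through.** **The plan's own figure.** The only number in the statistical section is the sample size of 80, set against 120 clinic attenders in 2019: 80/120 = 66.7%. No eligibility rate, consent rate or precision target is given, so the plan has no sphincter precision figure to reproduce. The point does not depend on the 80.

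**The text set side by side.**

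- Order: section 4.2 puts the examination before the scan, and section 4.1 puts the scan last at follow-up. Wound findings therefore exist by the time of scanning.
- Repetition: section 4.1 makes visits weekly until healing. Earlier scores therefore exist by the time of later ones.
- Outcome: section 4.2 uses a graded score, and section 2 makes it the basis of both secondary objectives.
- Safeguards: coding and anonymisation (sections 4.2, 5.1.1 and 5.2.2) serve confidentiality. Section 4.2 gives the clinical and research team access to the electronic data. Training in section 4.4.1 covers the plan and the site file only.

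No safeguard in this list separates scoring from what is known about the woman.

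**How fragile the first secondary objective is to any misreading.** All inputs here are assumptions: n women with an intact sphincter (the documents give no share, so 40 to 80 is used), k follow-up scans, and a rate f of false new-defect readings per scan.

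- Per woman: p = 1 − (1 − f)^k
- Expected false cases: n × p
- Chance of at least one: 1 − (1 − p)^n

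With f = 1%, k = 1 gives p = 1%. This also describes weekly readings that simply repeat the first one. With k = 4 independent readings, p = 1 − 0.99^4 = 3.94%.

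| n | k = 1: expected; chance of at least one | k = 4: expected; chance of at least one |
|---|---|---|
| 40 | 0.4; 33% | 1.6; 80% |
| 60 | 0.6; 45% | 2.4; 91% |
| 80 | 0.8; 55% | 3.2; 96% |

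At n = 60, f of 0.5%, 2% and 5% gives a chance of 26%, 70% and 95% with k = 1, and of 70%, 99% and about 100% with k = 4.

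For comparison, no cases in 60 women would support a one-sided 95% upper limit of 1 − 0.05^(1/60) = 4.9%. For 40 and 80 women the limits are 7.2% and 3.7%. One misread woman replaces that statement with a reported case.

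**What this does not show.** The rate f covers false readings from every cause. A masked reader with the same f gives the same table. It shows how little misreading the question tolerates, not how much unmasking adds.

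**The case against.** The strongest reply is that silence is not procedure. The plan gives an ordinary clinical sequence and never says that the examiner scores the scan, or that scoring is done live. Section 3, which by the table of contents covers site staff, was not in the text available and may assign roles. This stands. A reader might infer that the plan has the scan scored by whoever has just examined the wound; the documents do not say so. What remains is that the methods sections, where masking would normally appear, leave it open.

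A reader might also infer a direction, with bad wounds drifting towards defects and late visits towards recovery. The documents do not support that. Expecting an intact sphincter could equally hide a new defect.

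Nor can counts of false cases be offered as the effect of unmasking, for the reason given at the end of the working. A confidence interval that excludes zero proves nothing here either, since an exact interval does so as soon as one case is seen.

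The score is described as validated, and its structure may limit drift. Validation of a scale does not, however, protect a reading from what the reader already knows.

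Finally, a single scorer who rereads later may remember some women, and masking does not remove random reading error. Both are true. The first limits the remedy without defeating it. The second is why duplicate reads belong in it.

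**Conclusion.** The concern holds in a limited form. The reader is not identified, and nothing in the available text masks the reading to the examination, the sphincter status at delivery or the visit order. This leaves the aim and both secondary objectives open to bias of unknown direction and a size that the documents cannot supply. The question about intact sphincters is the more exposed, because a few misreadings either way could settle it.

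The conclusion rests on two premises: that scoring needs judgement, and that section 3 contains no masking rule. It should be fixed but is not critical, because the primary objective does not rest on scan reading.

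**What to change.** Add to section 4.2:

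- Every 3D ultrasound volume is stored under a code that carries no visit date, visit number or sphincter injury status.
- After the woman's last visit, or in later batches across women, the study's existing scorer reads the stored volumes in shuffled order without the examination record.
- Endoanal volumes are scored with the Starck score. Transperineal volumes are scored by one method fixed in advance and reported separately, because the plan gives the Starck score for endoanal scans only.
- The masked scores are used for the sphincter objectives. Live readings serve clinical care only.
- A random 10-20% of volumes enter the list twice, and same-reader repeatability is reported.

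The cost is a short amendment, image storage and reading time. If each woman had five scans (an assumption), there would be 80 × 5 = 400 volumes, plus 40 to 80 duplicate reads. No extra visit, scan or reader is needed. Batching across women lengthens the gap between live and masked reading and so reduces recall, but masking by the same person stays imperfect and the report should say so. The rule needs to be in place before scanning proceeds, because a volume that was not stored cannot be reread.

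### Do the weekly MolecuLight images lack the swab cultures that are meant to support them?

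*Combined protocol and SAP*

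**What the plan says.** Under the MolecuLight heading of Section 4.2 the protocol states: "The bacterial load of the perineal wound will be measured every week using the MolecuLight i:X". After describing the fluorescence colours it continues: "These findings will be supported by microbiological analysis of the wound with swab culture and sensitivity". It gives no timing, frequency or pairing for those cultures.

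Under the microbiological heading of the same section the swab rule reads: "If a wound swab has not been taken prior to referral or wound swab results are not available, one will be taken". Its stated purpose is to find the causative organisms, and the next sentence is: "Appropriate antibiotics will then be given to cover the detected organism".

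Section 4.1 sets the visit pattern: "Patients will be assessed at weekly intervals until the wound infection has resolved and the wound has clinically healed". It then lists what happens, beginning with the form and the examination. The imaging step comes next: "Following this, the wound will be photographed with the MolecuLight i:X Imaging Device". Silhouette mapping is added where the wound has superficially dehisced, and the list closes with the scan: "Finally, an endoanal ultrasound scan and/or transperineal ultrasound will be performed". No swab appears in that list.

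Section 4.2 also has antibiotic use recorded at baseline. The documents do not show the contents of the case report form completed at follow-up.

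**The concern.** The images form a weekly series, while the swab rule reads as a single event. A woman who arrives with an available result has no study swab under that rule, so her only culture predates every study image. For the others, the one swab falls near the start, and antibiotics chosen from its result follow. A red or cyan image several weeks later could then be described as culture-supported on the strength of a specimen taken before treatment.

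This would matter because the colour key in Section 4.2 is not unambiguous: dark and white areas have several possible causes, including poor lighting and objects in view. Culture is the plan's own check on the camera. The weekly images also bear on the primary objective, which is how the infection evolves clinically. If antibiotic dates after baseline were not recorded, a reader could not tell which images came before treatment and which after.

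**Working it through.** The protocol gives no figure for image-culture pairs, so there is none to reproduce. The check has two parts: a count under the strict reading, and a comparison of the relevant statements.

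**Inputs**
- Women enrolled: 80 (Section 4.5).
- Imaging: weekly until healed (Sections 4.1 and 4.2). The number of images per woman, k, is not given; I assume 1, 2, 4 and 8.
- Share of women referred with an available swab result, f: not given; I assume 0, 0.5 and 1.
- Strict reading, which is an inference: one study swab if there is no available result, otherwise none, and the swab is taken at a visit with imaging.

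**Count under the strict reading**
- Total images = 80k, giving 80, 160, 320 and 640 for k = 1, 2, 4 and 8.
- Maximum same-visit pairs = 80(1 − f), giving 80, 40 and 0 for f = 0, 0.5 and 1.
- Minimum images with no same-visit culture = 80k − 80(1 − f) = 80(k − 1 + f).
- Maximum share of images paired = (1 − f)/k.

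| f | k = 1 | k = 2 | k = 4 | k = 8 |
|---|---|---|---|---|
| 0 | 0 unpaired (100% paired) | 80 (50%) | 240 (25%) | 560 (12.5%) |
| 0.5 | 40 (50%) | 120 (25%) | 280 (12.5%) | 600 (6.25%) |
| 1 | 80 (0%) | 160 (0%) | 320 (0%) | 640 (0%) |

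If the first image is taken only after the swab visit, there are no pairs at any f or k. The number of pairs therefore runs from 0 to 80, which is every value the strict reading allows, so the count does not narrow the question.

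**Count under two other readings of the same text**
- Further swabs accompany the weekly images: up to 80k pairs and as few as 0 unpaired images.
- One culture per woman is enough: 80f women bring a result and 80(1 − f) are swabbed in the study. 80f + 80(1 − f) = 80, so a culture is sought for every woman whatever f is.

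**The statements side by side**
1. The swab rule says when a diagnostic swab must be taken. It sets a minimum for women without a usable result and does not forbid further swabs.
2. The support sentence sits under a different heading and serves a different purpose. It directly follows the account of what the colours signify, so it can refer to the fluorescence findings in general. It does not promise a culture for each image.
3. Section 4.1 is a summary of the design. It mentions no swab at any visit, not even the one that Section 4.2 plainly requires. Its silence is weak evidence that no later swabs are taken.
4. Section 4.2 says antibiotic use is obtained at baseline; it does not say only then. A case report form is completed at follow-up, and it may carry later dates.
5. The statistical paragraph in Section 4.2 names software only. No section plans an analysis of bacterial load, or of agreement between image and culture.

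**The case for a change.** The strongest case for a change is that the support sentence is a commitment with no schedule behind it, and that one reworded sentence and a few date fields would settle it at almost no cost. The textual part stands: the plan does not say which swab supports which images, and anyone writing up the image series would have to decide. It also stands that a culture taken before referral says little about an image taken weeks later, after treatment.

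The step from there to a defect does not stand. The limit of one swab per woman is read into a diagnostic rule, and the same-visit standard appears nowhere in the protocol. The possible misreporting of a late image supposes that individual images will be called culture-supported, which no section plans. The antibiotic point rests on a form that cannot be seen. A low cost of change is not a reason for one when no wrong result has been shown to follow from the plan as it is.

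**Conclusion.** The concern identifies missing detail, not an error. The timing of swabs relative to images is unstated, but the two statements in Section 4.2 are compatible on either of two ordinary readings: further swabs, or one culture per woman. The measure is a supporting one: bacterial load is not a named endpoint, the aim is sonographic, and neither secondary objective uses fluorescence.

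The unpaired counts, for example at least 240 of 320 images when k = 4 and f = 0, hold only under the strict reading and with assumed values of k and f. They measure no bias, and none is claimed in either direction. An analyst would fill the gap in the usual way, by giving the source and date of each culture and claiming support only where the dates allow it. The conclusion would be different if the plan named image-culture agreement or bacterial load as an outcome; it does not. No change to the plan follows.
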